3.1.5 Sample size for the annualized rate of brain volume loss (BVL)

We assume a normal distribution for the percentage brain volume change. Assuming a mean annualized rate of BVL of 0.45% on teriflunomide and 0.338% on ofatumumab (25% relative reduction) and a common standard deviation of 0.5%, a sample size of 621 patients with available MRI assessments would provide **80% power** at a one-sided alpha level of 0.025. Allowing from 20% dropouts, a total sample size of **778 randomized patients** are required for this endpoint (ca. 390 per arm).

3.1.6 Sample size for 3-month confirmed disability worsening (3mCDW)

For planning purposes only an exponential distribution of event times and proportional hazard is assumed. The cumulative event probability over two years is assumed as 15% vs 9.5% in patients treated with teriflunomide vs ofatumumab, respectively. The assumed cumulative event rates translate to a relative risk reduction of 38.6% (hazard ratio=0.614) in patients treated with ofatumumab compared with teriflunomide. The detection of a hazard ratio of 0.614 in a log-rank test with **90% power** at a one-sided alpha-level of 0.025-0.025² requires 178 qualifying events. Allowing for 20% dropouts over 2 years in both arms, a total sample size of **1774 randomized patients** is required. Assuming an accrual with 500 patients in the first 6 months, and 1500 patients per year thereafter, it is expected that accrual can be completed within approximately 18 months, and that the study duration is projected to last between 2.5 to 3 years.

For comparison to these assumptions, in the pivotal trials of teriflunomide, the cumulative probability of a 3-month confirmed disability worsening over 2 years in patients treated with teriflunomide 14 mg was 15.8% ([Confavreux et al. 2014](#)) and 20% ([O'Connor et al. 2011](#)), respectively. Furthermore, in combined ocrelizumab phase 3 studies ([Hauser et al. 2015](#)) the Kaplan-Meier estimates were 15.2 and 9.8 at year 2 for interferon beta-1a and ocrelizumab 600 mg, respectively; this corresponds to a hazard ratio 0.6 (40% relative risk reduction between ocrelizumab and interferon beta-1a).

3.1.7 Sample size for 6-month confirmed disability worsening (6mCDW)

The cumulative event probability over two years is assumed as 12% vs 7.548% in patients treated with teriflunomide vs ofatumumab, respectively. The assumed cumulative event rates translate to a relative risk reduction of 38.6% (hazard ratio=0.614) in patients treated with ofatumumab compared with teriflunomide. The detection of a hazard ratio of 0.614 in a log-rank test with **80% power** at a one-sided alpha-level of 0.025-0.025² requires 133 qualifying events. Allowing for 20% dropouts over 2 years in both arms, a total sample size of **1662 randomized patients** is required (831 per arm).

For comparison: In combined ocrelizumab Phase 3 studies (OPERA 1 and OPERA 2, [Hauser et al. 2015](#)) the Kaplan-Meier estimates were 12.0 and 7.4 at year 2 for interferon beta-1a and ocrelizumab 600 mg, respectively; this corresponds to a hazard ratio 0.6 (40% relative risk reduction between ocrelizumab and interferon beta-1a).

5.1 Imputation rules

5.1.1 Study drug

Missing or partial dates are not allowed in completing the study drug administration CRF pages. The end date of study drug will be the last end date or last injection date for patients randomized to teriflunomide or ofatumumab, respectively.

5.1.2 AE date imputation

For the start and end dates of the adverse event records, when incomplete or missing, dates will be imputed according to Novartis standards (details will be given in programming datasets specifications (PDS) document).

5.1.3 Concomitant medication date imputation

For the start and end dates of the concomitant medication records, when incomplete or missing, dates will be imputed according to Novartis standards (details will be given in programming datasets specifications (PDS) document).

5.1.3.1 Prior therapies date imputation

Same as above.

5.1.3.2 Post therapies date imputation

Same as above.

5.1.3.3 Relapse date imputation

Missing or partial dates are not expected for the start and end dates of relapses on the MS relapses CRF pages. In case partial dates (unknown day with month and year available) exist in the final database, the following rules will apply:

- For start date, it will be imputed by the first day of the month or the first dose date if it occurs in the same month as the first dose date.
- For end date, it will be imputed by the last day of the month or truncated to have a duration of maximally 90 days.

5.1.3.4 Other imputations

For the calculation of duration or time since relevant history events as specified in [Section 2.3.3](#) (MS disease baseline characteristics), partial dates will be imputed for the MS diagnosis start date, the first MS symptom date, the conversion to SPMS date, and the most recent relapse onset date via below imputation rules.

- If the year is missing or impossible (e.g. 12-Jan-1911), then the date will be imputed as missing.
- If the year is not missing and possible, but the month is impossible or missing (e.g. 17-XXX-2010), then the year will be kept and date will be imputed as July 1st (e.g., 1-July-2010).
- If the year and the month are not missing and possible, but the day is impossible or missing (e.g. 31-FEB-2009), then the year and month will be kept, and date will be imputed as 15th (e.g., 15-FEB-2009).
- The imputed dates should be prior to the screening visit date. That is, if imputed dates are on or after the screening visit date, the dates will be imputed to be one day before the screening visit date.

5.1.3.5 Data handling for relapses within 30 days of onset of previous relapses or relapses with duration beyond 90 days

According to protocol definition of MS relapses, the start date of a new relapse has to be at least 30 days after the start date of a previous relapse (i.e., start date of a new relapse – start date of a previous relapse ≥ 30). If a relapse is recorded with a start date less than 30 days after the start date of a previous relapse, below data manipulation will be done to combine them into a single relapse by creating a new relapse record with the following information.

- Start date: take the earliest start date.
- End date: take the latest end date. If one of the end dates is missing, set it to missing.
- Date of EDSS intended to confirm the relapse:
 - Take the date of EDSS by which the relapse can be confirmed.
 - If more than one EDSS assessments meet the above criteria, take the date of EDSS by which the worst severity value is derived.
 - If no EDSS assessment meets the above criteria, take the earliest date of EDSS as captured on the relapse CRF page.
- Severity: take the value representing the worst case (severe>moderate>mild>missing)
- “Did the relapse affect daily activities?”, “Hospitalization?”, “Steroid used?”, “Recovery status””: for each of these characteristics, take the value representing the worst case (yes>no for first 3 questions; no>partial>complete recovery for last question).

According to CRF completion guidelines, maximum duration of a relapse is 90 days. If a relapse is recorded with a duration longer than 90 days, the end date will be truncated to have a duration of exactly 90 days. This applies also to the artificial record created by above procedure. Missing end date of relapse is not allowed. In the rare cases that missing end date exist in the final database, it will be imputed so that the duration of relapse is exactly 90 days.

5.2 AEs coding/grading

AEs are coded using the Medical dictionary for regulatory activities (MedDRA) terminology. The latest MedDRA version will be used and will be described in the footnote of relevant outputs.

AEs will be assessed according to the Common Terminology Criteria for Adverse Events (CTCAE).

The CTCAE represents a comprehensive grading system for reporting the acute and late effects of cancer treatments. CTCAE grading is by definition a 5-point scale generally corresponding to mild, moderate, severe, life threatening, and death. This grading system inherently places a value on the importance of an event, although there is not necessarily proportionality among grades (a grade 2 is not necessarily twice as bad as a grade 1). The CTCAE grade of 5 (death) is not used; rather, ‘fatal’ is collected as AE outcome and death information is also collected on a separate (e)CRF page.

5.3 Laboratory parameters derivations

For each patient, the estimated creatinine clearance values (without collecting urine) will be calculated using the Cockcroft-Gault formula (as specified in [Table 5-1](#)). In these calculations, the body weight is the last measurement collected on or before the day when the patient takes the laboratory test and age should also be calculated based on the time when the patient takes the laboratory test.

If the creatinine value is collected in the unit $\mu\text{mol/L}$ (SI unit), it will be converted to mg/dL in order to use the formulas. The conversion is via the equation below:

- $\text{mg/dL} = 88.4 \mu\text{mol/L}$ (e.g., creatinine = 2.0 $\text{mg/dL} = 176.8 \mu\text{mol/L}$).

Table 5-1 Creatinine clearance calculation

Variable	Formula
Creatinine clearance [mL/min] using Cockcroft-Gault formula (Cockcroft and Gault 1976)	$= (140 - A) \times W / (72 \times C) \times G$ 
Where
 
A is age [years] W is body weight [kg] C is the serum concentration of creatinine [mg/dL] G is a constant: G=1 for males and G=0.85 for females.

The estimated creatinine clearance will be included as one of the laboratory parameters.

5.3.1 Laboratory test groups and subgroups

On presenting lab results, grouping parameters by family will ease the review. Table below shows a possible set of lab parameters and their corresponding classification.

Table 5-2 Laboratory tests

Order	Laboratory Group Subgroups	Tests [SI unit]
1	Hematology Red Blood Cells White Blood Cell Differential	Hematocrit [%] Hemoglobin [g/L] Platelets [10E9/L] Red cell count [10E12/L] Absolute Basophils [10E9/L] Absolute Eosinophils [10E9/L] Absolute Lymphocytes [10E9/L] Absolute Monocytes [10E9/L] Absolute Neutrophils [10E9/L] Basophils [%] Eosinophils [%] Lymphocytes [%] Monocytes [%] Neutrophils [%] White Cell Count [10E9/L]

Order	Laboratory Group Subgroups	Tests [SI unit]
	
B-cells
 
Immunoglobulin
	
CD19+ B-cell counts[cells/μL]
 
Total IgG [g/L]
 
Total IgM [g/L]

2	
Chemistry
 
Renal Function
 
Liver Function Tests
 
Other Enzymes
 
Lipids
 
Other
 
Electrolytes / Metabolism Tests
	
Creatinine [μmol/L]
 
Blood urea nitrogen [mmol/L]
 
ALT [U/L]
 
Albumin [g/L]
 
Alkaline Phosphatase [U/L]
 
AST [U/L]
 
Bilirubin (direct/conjugated) [μmol/L]
 
GGT [U/L]
 
Total Bilirubin [μmol/L]
 
Total protein [g/L]
 
Amylase [U/L]
 
Cholesterol HDL [mmol/L]
 
Cholesterol LDL [mmol/L]
 
Triglycerides [mmol/L]
 
Total Cholesterol [mmol/L]
 
Random glucose [mmol/L]
 
C-Reactive protein (CRP) [mg/L]
 
Bicarbonate [mmol/L]
 
Calcium [mmol/L]
 
Chloride [mmol/L]
 
Magnesium [mmol/L]
 
Phosphate [mmol/L]
 
Potassium [mmol/L]
 
Sodium [mmol/L]

3	
Urinalysis
	
Blood
 
Glucose
 
Specific gravity
 
Albumin
 
Protein

5.3.2.1 Definition of characteristics for liver event overview summary

Characteristics: Liver events are categorized based on ALT and ALP measurements using the closest lab assessment +/- 7 days from the onset of the liver event into the following characteristics ‘Hepatocellular’ (ALT > 2xULN or ALT/ULN:ALP/ULN > 5), ‘Cholestatic’ (ALP > 2xULN or ALT/ULN:ALP/ULN ≤ 2), ‘Mixed’ (ALT > 2xULN and ALP > ULN and 2 < ALT/ULN:ALP/ULN ≤ 5), ‘None’ (if none of the three above qualifies), and ‘Unknown’ (in case of a missing ALT or ALP values). Note that the categories are not mutually exclusive. The definition is consistent with Novartis safety guideline on hepatotoxicity.

5.3.3 CTCAE grades for laboratory parameters

Table 5-3 CTCAE grades for laboratory parameters (CTCAE Version 5)

		Grade			
Abnormality	Lab parameter	1	2	3	4
Hematology					
Anemia	Hemoglobin (g/L)	<LLN - 100 g/L	<100 - 80 g/L	<80 g/L transfusion indicated	

		Grade			
Abnormality	Lab parameter	1	2	3	4
Platelet count decreased	Platelets (thrombocytes) (10 ⁹ /L)	<LLN-75.0 x 10 ⁹ /L	<75.0 - 50.0 x 10 ⁹ /L	<50.0 - 25.0 x 10 ⁹ /L	<25.0 x 10 ⁹ /L
White blood cell decreased	Leukocytes (WBCs) (10 ⁹ /L)	<LLN - 3.0 x 10 ⁹ /L	<3.0 - 2.0 x 10 ⁹ /L	<2.0 - 1.0 x 10 ⁹ /L	<1.0 x 10 ⁹ /L
Neutrophil count decreased	Absolute neutrophil count (10 ⁹ /L)	<LLN - 1.5 x 10 ⁹ /L	<1.5 - 1.0 x 10 ⁹ /L	<1.0 - 0.5 x 10 ⁹ /L	<0.5 x 10 ⁹ /L
Lymphocyte count decreased	Absolute lymphocyte count (10 ⁹ /L)	<LLN x 0.8 - 10 ⁹ /L	<0.8 - 0.5 x 10 ⁹ /L	<0.5 - 0.2 x 10 ⁹ /L	<0.2 x 10 ⁹ /L
Lymphocyte count increased	Absolute lymphocyte count (10 ⁹ /L)		>4 - 20 x 10 ⁹ /L	> 20 x 10 ⁹ /L	
Chemistry					
Liver function					
Alanine aminotransferase increased	ALT (SGPT) (U/L)	>ULN - 3.0 x ULN if baseline was normal; >1.5 - 3.0 x baseline if baseline was abnormal	>3.0 - 5.0 x ULN if baseline was normal; >3.0 - 5.0 x baseline if baseline was abnormal	>5.0 - 20.0 x ULN if baseline was normal; >5.0 - 20.0 x baseline if baseline was abnormal	>20.0 x ULN if baseline was normal; >20.0 x baseline if baseline was abnormal
Aspartate aminotransferase increased	AST (SGOT) (U/L)	>ULN - 3.0 x ULN if baseline was normal; 1.5 - 3.0 x baseline if baseline was abnormal	>3.0 - 5.0 x ULN if baseline was normal; >3.0 - 5.0 x baseline if baseline was abnormal	>5.0 - 20.0 x ULN if baseline was normal; >5.0 - 20.0 x baseline if baseline was abnormal	>20.0 x ULN if baseline was normal; >20.0 x baseline if baseline was abnormal
Blood bilirubin increased	Bilirubin (µmol/L)	>ULN - 1.5 x ULN if baseline was normal; >1.0 - 1.5 x baseline if baseline was abnormal	>1.5 - 3.0 x ULN if baseline was normal; >1.5 - 3.0 x baseline if baseline was abnormal	>3.0 - 10.0 x ULN if baseline was normal; >3.0 - 10.0 x baseline if baseline was abnormal	>10.0 x ULN if baseline was normal; >10.0 x baseline if baseline was abnormal
GGT increased	Gamma-glutamyl transferase (GGT) (U/L)	>ULN - 2.5 x ULN if baseline was normal; 2.0 - 2.5 x baseline if baseline was abnormal	>2.5 - 5.0 x ULN if baseline was normal; >2.5 - 5.0 x baseline if baseline was abnormal	>5.0 - 20.0 x ULN if baseline was normal; >5.0 - 20.0 x baseline if baseline was abnormal	>20.0 x ULN if baseline was normal; >20.0 x baseline if baseline was abnormal
Alkaline phosphatase increased	Alkaline Phosphatase	>ULN - 2.5 x ULN if baseline	>2.5 - 5.0 x ULN if baseline was	>5.0 - 20.0 x ULN if baseline was	>20.0 x ULN if baseline was

		Grade			
Abnormality	Lab parameter	1	2	3	4
	(U/L)	was normal; 2.0 – 2.5 x baseline if baseline was abnormal	normal; >2.5 – 5.0 x baseline if baseline was abnormal	normal; >5.0 – 20.0 x baseline if baseline was abnormal	normal; >20.0 x baseline if baseline was abnormal
Renal function Note: A semi-colon (;) indicates 'or' within the description of the grade.					
Creatinine increased*	Creatinine (µmol/L)	>ULN - 1.5 x ULN	>1.5 - 3.0 x baseline; >1.5 - 3.0x ULN	>3.0 baseline; >3.0 - 6.0 x ULN	>6.0 x ULN
Other enzymes					
Serum amylase increased	Amylase (U/L)	>ULN - 1.5 x ULN	>1.5 - 2.0 x ULN; >2.0 - 5.0 x ULN and asymptomatic	>2.0 - 5.0 x ULN with signs or symptoms; >5.0 x ULN and asymptomatic	>5.0 x ULN and with signs or symptoms
Serum amylase** increased	Amylase (U/L)	>ULN - 1.5 x ULN	>1.5 - 2.0 x ULN;	>2.0 - 5.0 x ULN	>5.0 x ULN
Lipids					
Cholesterol high	Cholesterol Total (mmol/L)	>ULN- 7.75 mmol/L	>7.75-10.34 mmol/L	>10.34-12.92 mmol/L	>12.92 mmol/L
Hypertriglyceridemia	Triglycerides (mmol/L)	1.71 - 3.42 mmol/L	>3.42 - 5.7 mmol/L	>5.7 - 11.4 mmol/L	>11.4 mmol/L
*Highest grade will be assigned if more than one grade criteria are met for an observed value of a patient.					
**CTCAE 4.03 definition. For reporting in CSR, the grade definition per CTCAE 4.03 will be used for this parameter only.					

5.4 Clinical notable vital signs

Clinically notable vital sign values to be used for this study are listed below.

Table 5-4 Vital signs clinically notable values

Vital Sign	Notable criteria
Pulse (beats/min, bpm)	>120 bpm Or <50 bpm
Systolic Blood Pressure (mmHg)	≥160 mmHg Or ≤90 mmHg

Vital Sign	Notable criteria
Diastolic Blood Pressure	≥ 100 mmHg Or ≤ 50 mmHg
Temperature ($^{\circ}\text{C}$)	>38.3 $^{\circ}\text{C}$ (>101 $^{\circ}\text{F}$)
Body weight (kg)	$\geq 7\%$ from baseline weight

5.5 Statistical models

5.5.1 Primary analysis

The null hypothesis is that there is no difference in the ARR between ofatumumab 20mg sc once monthly and teriflunomide 14 mg po once daily in reducing the frequency of confirmed MS relapses as measured by ARR. The alternative hypothesis is that there is a difference between the two treatment groups. $H_0: \text{ARR}_o/\text{ARR}_t = 1$ vs. $H_a: \text{ARR}_o/\text{ARR}_t < 1$. Where ARR_o and ARR_t are ARR of ofatumumab and ARR of teriflunomide respectively.

The null hypothesis will be tested using a negative binomial regression model with log-link, treatment and region as factors, number of relapses in previous year, baseline EDSS, baseline number of T1 Gd-enhancing lesions and the patient's age at baseline as covariates.

The SAS procedure GENMOD will be used to conduct the analysis. In GENMOD, the log of the dispersion parameter will be used (lognb) as an option in model statement. The natural log of time in year is used as an offset by specifying offset option in the model statement.

5.5.2 Key secondary analysis

For disability related key secondary endpoints, the Cox proportional hazard model will be the key secondary analysis to test $H_0: \lambda_o/\lambda_t = 1$ vs. $H_a: \lambda_o/\lambda_t < 1$. Where λ_o and λ_t are hazard of disability events in ofatumumab and teriflunomide treatment groups respectively. A stratified Cox proportional hazards model with study as stratum, treatment, and region as factors and baseline EDSS at baseline as a continuous covariate. The model will contain a treatment-by-study interaction.

The Cox proportional hazard (PH) model assumes that the effect of each covariate is the same at all points in time. To check the PH assumption for the treatment covariate, a plot of log-log survivor function vs. time for each treatment group will be used. If the hazards are proportional, the log-log survivor functions should be parallel. Approximate parallelism between the curves for the treatment groups will provide supportive evidence of the proportional hazards assumption.

If the assumption of proportional hazards is questionable based on graphical analyses, then the interpretation of the estimated hazard ratio will need to be done with caution.

The SAS procedure PHREG will be used to conduct the Cox PH analysis. The SAS procedure LIFETEST will be used to conduct the KM analysis.

For the key secondary endpoints related to Gd lesions and T2 lesions, mathematical details are similar to the ones for primary analysis described in [Section 5.5.1](#) as the negative binomial models will be used.

For the key secondary endpoint related to brain volume change, a random coefficients model will be used to test $H_0: \beta_o - \beta_t = 0$ vs. $H_a: \beta_o < \beta_t$. Where β_o and β_t are annual rate of percent change from baseline in brain volume in ofatumumab and teriflunomide treatment groups respectively. The random coefficients model will include treatment, region as fixed effects (factors), and time, number of Gd-enhancing lesions at baseline, baseline T2 volume, and normalized brain volume at baseline as continuous covariates. Time as a continuous covariate allows for estimation of different slopes and intercepts among treatment groups. The model will also contain random terms to account for deviations about the population slope and intercept. The annual rate of percent change from baseline in brain volume is approximates as the population slope within the treatment group.

Percent brain volume change was approximately linear over time and approximately normally distributed in 3 independent studies of the fingolimod phase 3 program. Data collected from this study will be checked descriptively by plotting the population mean percent change from baseline against time before database lock in a blinded fashion (pooling all patients).

The SAS procedure MIXED will be used to conduct the analysis. Unstructured covariance will be assumed.

5.5.3 Important supportive analysis of primary or key secondary endpoints

5.5.3.1 Supportive analysis of primary endpoint:

To estimate the ARR and the treatment effect during the initial “onset of action” period of 8 week (≤ 56 days = $8 * 7$ days), and the ARR and the treatment effect thereafter (> 56 days; long-term efficacy) a sensitivity analysis will be conducted on the FAS. The number of confirmed relapses for the i^{th} patient from treatment group j who spent t_i years in the study $N_{ij}(t_i)$ is assumed to follow a piecewise constant negative binomial distribution with different ARR before and after day 56 but with a constant dispersion k .

$$N_{ij}(t_i) = N_{ij}(t_i^1) + N_{ij}(t_i^2) \quad \text{where} \quad \begin{cases} N_{ij}(t_i^1) \sim \text{NegBin}(\lambda_j^1 * t_i^1, k), & t_i^1 \leq 56 \\ N_{ij}(t_i^2) \sim \text{NegBin}(\lambda_j^2 * t_i^2, k), & t_i^2 = t_i - 56 \quad \text{for } t_i > 56 \end{cases}$$

In the above notation, t_i^1 and t_i^2 are the times spent in the study before and after day 56 respectively. The total time in study $t_i = t_i^1 + t_i^2$.

5.5.3.1.1 Implementation in SAS

The piecewise constant negative binomial regression model can be re-written as a Poisson-Gamma mixture model which can be implemented in SAS via NLMIXED procedure. Specifically, let $N_{ij}(t_i)|U_i$ denote a Poisson distributed random variable where U_i is a Gamma distributed random variable with mean 1 and variance $1/\alpha = k$. The model assumed for the mean of $N_{ij}(t_i)|U_i$ is expressed by time period, before t_i or after day 56 respectively:

$$\begin{cases} E(N_{ij}(t_i^1) | U_i) = \lambda_1^1 \cdot t_i^1 \cdot \exp(\theta^1 \cdot trt_j + x_i^T \gamma) \cdot U_i, & t_i^1 \leq 56 \text{ days} \\ E(N_{ij}(t_i^2) | U_i) = \lambda_1^2 \cdot t_i^2 \cdot \exp(\theta^2 \cdot trt_j + x_i^T \gamma) \cdot U_i, & t_i^2 = t_i - t_i^1 \text{ and } t_i > 56 \text{ days} \end{cases}$$

Where x_i^T denotes the vector of covariates for subject i , and trt_j is an indicator variable which is one for all patients assigned to ofatumumab and zero for those assigned to teriflunomid, $\exp(\gamma)$ quantifies the effect of the covariates. Thus, λ_1^1 and λ_1^2 represent the ARR for teriflunomid up to day 56 and thereafter, respectively. The treatment effect (ARR-ratio) is $\exp(\theta^1)$ during the first 56 days, and $\exp(\theta^2)$ thereafter. Hence, the ARR on ofatumumb is $\lambda_2^1 = \lambda_1^1 \exp(\theta^1)$ during the first 56 days, and $\lambda_2^2 = \lambda_1^2 \exp(\theta^2)$ thereafter.

In case of non-convergence of this model, all covariates will be dropped from the model.

As the annualized relapse rate is to be estimated, time will be divided by 365.25 (as in year scale) for implementation in SAS. The data set will be prepared in such a way that there will be 2 records, one for period ≤ 56 days and the other for period > 56 days, for patients whose actual time in study is greater than 56 days. For period ≤ 56 days, the number of confirmed relapses with relapse starting date on or before day 56 will be calculated and the time in study variable will be set to 56/365.25. For period > 56 days, the number of confirmed relapses with relapse starting date after day 56 will be calculated and the time in study variable will be set to (value of time in study overall-56 then divided by 365.25). The time period indicator variable will be populated for both records appropriately (e.g., 0 for period ≤ 56 days and 1 for period > 56 days). For patients whose actual time in study variable is ≤ 56 days, the observed record (i.e., same as the overall number of confirmed relapses and time in study) will be populated with time period indicator as ≤ 56 days. [Table 5-5](#) provides an example of the data set where other covariates are to be added accordingly.

Table 5-5 Key data structure for piecewise NB model

Patient	Treatment	Treatment code	Period code	Time in study (total)	Time in study (by period)	No. of confirmed relapses (total)	No. of confirmed relapses (by period)
1	OFA20	1	0	100/365.25	56/365.25	3	1
1	OFA20	1	1	100/365.25	44/365.25	3	2
2	TER14	0	0	45/365.26	45/365.26	2	2

Additional patient level variables will be derived to be used as covariates in this model.

Continuous covariates will be centered by the mean. For example, age will be centered by subtracting the mean of age as $(age - \text{mean}(\text{age}))$. The mean will be calculated based on all patients in the study.

Factors will be dummy coded. There are 3 factors in the model, i.e. treatment, period, and region. Treatment code and Period code as shown in [Table 5-5](#) can be considered as dummy

coded variables as each factor has 2 levels only where the reference level will have a value of 0. Region will have 5 levels (as in [Section 5.8](#)) so that 4 dummy coded region variables will be derived. The reference region will be the “North America and AUS” region. The rest 4 regions will each have a dummy coded variable with value of 1 if patients are in this region or 0 if patients are not in this region. Patients in the reference region will have 0 values in all 4 region dummy coded variables.

5.5.3.2 Supportive analysis of key secondary endpoints (3mCDW and 6mCDW):

To estimate the hazard ratio between treatment groups during the initial “onset of action” period of 8 weeks (≤ 56 days= $8*7$ days), and thereafter (>56 days; long-term efficacy) a sensitivity analysis will be conducted for the 3mCDW and 6mCDW. A stratified Cox proportional hazards model similar to that for the main analysis will be used with study and time period indicator as strata, treatment and region as factors and baseline EDSS as a continuous covariate. The model will also contain an interaction term of time period indicator by treatment.

The SAS procedure PHREG will be used to conduct the analysis.

The data set for Cox’s PH model will include a time to event variable and event status variable (0 as censored) as usual. To fit the above mentioned stratified Cox’s PH model, an artificial record will be created for patients whose actual time to event variable is >56 days. This artificial record will set the time to event variable equal to 56 days and event status variable as censored. A time period indicator variable will be populated for all records as 0 if the time to event variable ≤ 56 days and 1 if the time to event variable >56 days. [Table 5-6](#) provides an example of the data set where other covariates are to be added accordingly. **Bolded** records are artificial records.

Table 5-6 Key data structure for stratified Cox’s PH model

Patient	Treatment	Treatment code	Period code	Time to event	Event status
1	OFA20	1	0	56	0
1	OFA20	1	1	100	1
2	TER14	0	0	45	1
3	OFA20	1	0	56	0
3	OFA20	1	1	155	0

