9.4.3 Sensitivity analyses

The primary analysis will be repeated based on all reported MS relapses (rather than on only the confirmed ones).

The primary analysis will be repeated using the per-protocol set to provide an analysis of on-treatment data from subjects who have no major protocol violations. Relapses which occurred after permanent discontinuation of study medication will be excluded and natural log (time on study drug in years) rather than natural log (time on study in years) will be used as the offset variable in the negative binomial model.

To estimate relapse rates and the treatment effect between ofatumumab 20 mg sc once monthly and teriflunomide 14 mg po once daily during the initial “onset of action” period of 8 weeks (≤ 56 days= $8*7$ days), and relapse rates and the treatment effect thereafter (> 56 days; long-term efficacy) a sensitivity analysis will be conducted. This analysis will be implemented as a piecewise negative binomial model assuming different event rates and ARR-ratios before and after week 8, but constant dispersion. Per patient, 2 cumulative count-records (confirmed relapses ≤ 56 days, and > 56), and 2 corresponding time records (time-in-study ≤ 56 days, and > 56) will be calculated. The negative binomial model will be defined with the number of confirmed relapses as the response variable, with log-link and time-in-study as the offset variable. The model will use the same factors and covariates as the primary model.

For each time period (≤ 56 days, and > 56 days), the adjusted ARR (i.e., model-based estimate adjusted for covariates) and the corresponding 95% confidence intervals will be provided by treatment, together an ARR ratio between ofatumumab 20 mg sc once monthly and teriflunomide 14 mg po once daily (also expressed as percentage reduction relative to control group) with corresponding 95% confidence intervals and p-values.

Additionally, the time-to-first relapse will be analyzed in a Cox proportional hazards model. In comparison with the primary analysis in a negative binomial model, the Cox proportional hazards model does not assume constant relapse rates (but rather it assumes proportional hazards). The Cox proportional hazards model will be specified with treatment, region, number of relapses in previous year, baseline EDSS, baseline number of T1 Gd-enhancing lesions and the patient's age at baseline as covariates.

Additional sensitivity analyses may be defined in the analysis plan prior to database lock.

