Statistical models will include adjustments for regions by pooling centers to regions. The definition of region is intended to correspond to that used for the stratification of the randomization (as defined in [Section 5.8](#)). However, the definition of region may be modified if that is indicated based on statistical criteria (e.g., non-convergence). For statistical analysis where region is adjusted in the statistical models, regions “Asia Pacific” and “Latin America” will be combined with region “Other” due to small number of patients in these 2 regions.

Presentation of p-values: p-values from statistical tests will be presented with 3 decimal places, or as <.001 where applicable. Statistically significant p-values will be flagged with an asterisk. In general, this is when p-values ≤ 0.05 . For key-secondary disability-related hypotheses, two asterisks will be used if p-value ≤ 0.04875 ($=2*[0.025-0.025*0.025]$) as these hypotheses will be tested at alpha minus alpha-squared (this condition will be footnoted on the relevant outputs).

All data (collected or derived) will be listed appropriately.

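### The piecewise relapse model reports each arm's ARR at the reference region and trial-mean covariates, not averaged over the trial's regions

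*SAP*

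**What the plan says.** SAP 5.5.3.1.1 writes the piecewise negative binomial model as a Poisson-gamma mixture. In each period the mean is λ·t·exp(θ·trt + x′γ)·U, where x "denotes the vector of covariates for subject i" and U is a frailty with mean 1. The two λ parameters are said to "represent the ARR for teriflunomid up to day 56 and thereafter, respectively", and the ofatumumab ARR is λ·exp(θ).

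The coding rules follow in the same section. "Continuous covariates will be centered by the mean", and "The mean will be calculated based on all patients in the study". Region is a dummy-coded factor with North America and AUS as reference: "Patients in the reference region will have 0 values in all 4 region dummy coded variables". The section gives region five levels and cites SAP 5.8.

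SAP 2.5.5 asks for an adjusted ARR with a 95% confidence interval by treatment and period, and SAP 2.7.1 takes the secondary endpoint of ARR beyond 8 weeks from this model. Protocol 9.4.3 adds: "The model will use the same factors and covariates as the primary model". SAP 2.1 merges Asia Pacific and Latin America into Other for all region-adjusted models, "due to small number of patients in these 2 regions".

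**The concern.** Centring the continuous covariates makes λ a trial-average rate with respect to those covariates. Region did not get the same treatment, and no later step averages over it. The table would therefore carry, under the label of the arm's ARR, a value that belongs to one region's intercept. A reader will set that value beside the adjusted ARR from the primary model and beside the rate in the other period.

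The non-convergence rule adds a further wrinkle. It drops all covariates, so the same table cell would change from a reference-region rate to an all-region rate.

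Separately, the region factor described here does not match the one that SAP 2.1 prescribes.

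**Working it through.** The plan states no figure for this quantity, so there is none to reproduce. The check is algebra on the SAP's own model, then a numerical confirmation.

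**1. What λ is.** Set trt = 0 and x = 0. Because U has mean 1, E(N) = λ·t. The continuous part of x is zero at the all-patient mean. The region part is zero only in North America and AUS. So λ is the teriflunomide rate in that region at trial-mean age, EDSS, prior relapses and Gd lesions.

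**2. What a trial-wide rate would be.** With region shares w_r and region effects γ_r (γ = 0 for the reference), the rate standardised over regions is λ·Σ w_r·exp(γ_r). It equals λ only if the region effects are nil or cancel.

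**3. What does not change.** "The treatment effect (ARR-ratio) is" exp(θ) in each period. Moving the evaluation point multiplies both arms by the same factor, which cancels in the ratio.

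**4. Scale (assumed, not from the documents).** Take the planning rates 0.28 and 0.168 as the trial-wide values, and let the reference region's rate be 0.7 to 1.3 times the trial average:

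- teriflunomide: 0.28 × 0.7 = 0.196 and 0.28 × 1.3 = 0.364, reported as 0.20 to 0.36;
- ofatumumab: 0.168 × 0.7 = 0.118 and 0.168 × 1.3 = 0.218, reported as 0.12 to 0.22;
- ratio: 0.6 at either end.

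**5. Numerical confirmation.** The same mixture model was fitted by maximum likelihood to one simulated data set of 40,000 patients. The assumptions were four regions with shares 20/25/40/15% (reference first), region rate ratios 1/1.2/1.6/1.4, dispersion 0.82, 1.5 years of follow-up, a true reference-region teriflunomide rate after day 56 of 0.20, and a true ARR ratio of 0.6. Teriflunomide after day 56:

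| Quantity | Value |
|---|---|
| λ as coded in the SAP | 0.193 |
| Crude rate, reference region | 0.191 |
| Crude rate, all regions | 0.275 |
| Rates averaged by observed region shares | 0.271 |
| Region dummies centred on observed shares | 0.266 |
| Region terms averaged with equal weights | 0.256 |

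The fitted ARR ratio was 0.599 with uncentred and with centred dummies. λ tracks the reference region, and the last three rows show that the choice of weights also moves the answer.

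**6. Region levels.** SAP 5.8 lists six regions. Merging two of them into Other under SAP 2.1 leaves 6 − 2 = 4 levels, hence three indicators. SAP 5.5.3.1.1 has five levels and four indicators, which matches neither.

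**The case against.** The best reply is that nothing inferential depends on this. The secondary objective asks whether ofatumumab is superior on ARR beyond 8 weeks, and the ratio with its interval and p-value answers that. The analysis also lies outside the testing hierarchy of SAP 2.5.3. This stands. A reader might infer that the superiority conclusion or type I error is at risk; the documents do not support that.

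A second reply is that the SAP describes a parameterisation rather than code, and that a programmer could satisfy SAP 2.5.5 with a suitable ESTIMATE statement. That is possible, but the section itself identifies λ as the ARR, so reporting λ is the natural reading. No other text sets an evaluation point or region weights.

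Third, a reader might infer that the primary adjusted ARR is the trial's rate and that only the piecewise one departs from it. SAP 2.5.2 and 5.5.1 do not say how the primary estimate weights regions, so this cannot be assumed. Centring the dummies on observed shares could therefore create a new mismatch with the primary estimate.

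Fourth, the value should not be read as North America/Australia's own observed ARR. It is that region's model rate at trial-mean continuous covariates.

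Finally, the model already adjusts for four prognostic covariates, so only residual regional differences matter, and these could be nil. If the non-convergence fallback is used, the issue disappears.

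**Conclusion.** The point holds for the per-arm absolute ARRs and their confidence intervals in both periods. As specified, they describe the reference region at trial-mean continuous covariates and are labelled as the arm's ARR. This follows from the stated coding alone and needs no assumption about the data.

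The size and direction of any gap from a region-averaged rate do need assumptions, because the documents give neither region shares nor regional rates. The 0.7 to 1.3 range illustrates scale; it does not demonstrate a bias.

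The region count is a genuine inconsistency but a separate one. The general rule in SAP 2.1, together with the Protocol's requirement to use the primary model's factors, settles it at four levels. The per-arm rates will be reported for a named secondary endpoint, so the text should be corrected.

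**What to change.** In SAP 5.5.3.1.1, obtain each by-arm, by-period ARR from an ESTIMATE statement that adds to log λ (or log λ + θ) the region coefficients averaged with one stated set of region weights, and then exponentiates. State the same weights for the adjusted ARR of the primary model in SAP 2.5.2 and 5.5.1, and use them in both. Averaging on the log scale gives a geometric rather than an arithmetic mean over regions, so name the scale and keep it the same in both models. Centre the region dummies on FAS shares only if those shares are the chosen weights.

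Replace the five levels and four indicators with the four merged regions of SAP 2.1 (Western Europe, Eastern Europe, North America and AUS, and Other including Asia Pacific and Latin America) and three indicators.

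The cost is a few sentences in the SAP and a few lines of NLMIXED and GENMOD code. No new data or protocol change is needed.
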